#### **1.4 Correlative Objectives**

- 1.4.1 To characterize a broad array of immune markers in metastatic HR-positive breast tumors (characterization will be based on histology, protein expression, and mRNA expression)
- 1.4.2 To explore how different immunosuppressive and/or immune-stimulating immune marker profiles at baseline vary between patients with and without response (response assessed by RECIST 1.1 and immune-related response criteria)
- 1.4.3 To characterize serial changes in immune marker profile in peripheral blood mononuclear cells (PBMCs) over the course of the trial treatment
- 1.4.4 To explore whether induction of changes in the immunosuppressive and/or immune-stimulating immune marker profile in PBMCs vary between patients with and without response (response assessed by RECIST 1.1 and irRECIST criteria)
- 1.4.5 To investigate whether there is an immune marker in circulating PBMCs that corresponds to tumor infiltrating lymphocyte (TIL) percentage in baseline tumor
- 1.4.6 **In the cohort of patients who have re-biopsy at progressive disease (PD):** To characterize changes in a broad array of immune markers at time of progression (as characterized in aim 1.4.1) to time of progressive disease on trial therapy).
- 1.4.7 To collect blood to study cell-free DNA for comparison to tumor specimens.
- 1.4.8 To characterize the structure and function of the gut microbiome in patients with breast cancer prior to starting this clinical trial.
- 1.4.9 To determine whether pre-treatment characteristics of the structure and function of the gut microbiome in patients with breast cancer is associated with efficacy of pembrolizumab plus eribulin versus eribulin alone.
- 1.4.10 To characterize changes in the structure and function of the gut microbiome of patients with breast cancer after two cycles of therapy compared to baseline.
- 1.4.11 To determine whether changes in the overall diversity of the gut microbiome, estimated by the Shannon Index, of patients with breast cancer after two cycles of therapy regimens is associated with efficacy of pembrolizumab plus eribulin versus eribulin alone.
- 1.4.12 To determine if the abundance and functional profile of specific gut bacteria are associated with objective response to pembrolizumab plus eribulin.
- 1.4.13 To evaluate the functional pathways that may play a role as a predictive biomarker of response to pembrolizumab plus eribulin.

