## **9. BIOMARKER, CORRELATIVE, AND SPECIAL STUDIES**

All patients will be asked to provide archival tumor tissue (either paraffin blocks or 20 unstained slides, ideally 4 micron thickness). However, if archival tissue is not available or not evaluable, that will not be a basis to exclude the patient from any portion of the trial or the planned analysis. Archival tissue will be used for immune profiling assays to ascertain baseline values in patients who choose not to undergo baseline research fresh tissue biopsy or in whom there is insufficient tissue or failed testing of any of the planned assays from baseline fresh tissue biopsy.

If obtained, we plan to use baseline biopsy tissue to perform a number of immune profiling assays, detailed below, and characterize the samples based on histology (TILs), protein

expression, and mRNA expression. Additionally, specimens we will banked for possible future analysis.

Serial blood draws for correlative science are required on this trial; blood draws will be obtained every 3 weeks on treatment days prior to the infusion of study drugs, at the end-of-treatment visit in patients who go off study for progressive disease, and all efforts will be made to obtain a sample at the time of progressive disease from participants who went off study for anything other than progressive disease. We will perform flow cytometry on these samples to characterize protein expression of immune mediators as detailed in the lab manual. Circulating tumor DNA will be assessed as well.

An optional research biopsy will be collected for participants who have consented and have biopsy accessible tumor on arm B crossing over to pembrolizumab therapy.

An optional research biopsy at the time of progression will be collected for participants who consent and have biopsy accessible tumor. These biopsies will undergo the same characterization testing as described for baseline biopsies.

All patients will additionally be asked to provide a stool sample at three separate timepoints: prior to treatment, during treatment, and at the time of disease progression. A fourth collection may be requested from patients who experience grade  $\geq 2$  diarrhea after discussion with the PI. This collection is not required, but is strongly encouraged. These samples will be analyzed for microbiota content.

Please refer to the separate laboratory manual for additional correlative details including collection, processing, and shipping instructions.

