## **9.6 Hypothesis for correlative objectives**

### **9.6.1 Hypotheses**

- We hypothesize that the immune marker profile in the peripheral blood will change over the course of eribulin mesylate +/- pembrolizumab therapy.
- We hypothesize that a larger increase in markers of immune activity in the peripheral blood will correlate with a better disease response as assessed on concurrent restaging scans, and in terms of best radiographic response at any time on trial.  
We hypothesize that an immune marker or composite of markers in the peripheral blood at baseline will correspond to TIL percentage in archival tumor tissue.
- We hypothesize that the immune activity associated with a breast tumor, as assessed both in tumor tissue and in circulating blood, will be less at the time of disease progression on therapy compared to the time of therapy initiation.
- We hypothesize that the structure and function of the gut microbiome differs among patients with breast cancer.
- We hypothesize that the structure and function of the gut microbiome before starting pembrolizumab and eribulin can be predictive of efficacy of this therapy, with a greater microbial diversity, estimated by Shannon index, being predictive of efficacy.
- We hypothesize that the structure and function of gut microbiome changes in response pembrolizumab-based therapy and can predict the likelihood of response to pembrolizumab.
- We hypothesize that the abundance and functional profile of specific gut bacteria is associated with response to pembrolizumab.

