### **13.6.1 *Blood and tissue correlative science endpoints:***

- We will describe the presence and abundance of multiple immune markers in metastatic HR-positive breast tumors (characterization will be based on histology, protein

expression, and mRNA expression; see Section 9 for further details on characterization) using frequency tables and descriptive statistics (mean, standard deviation, median, and inter-quartile range).

- We will explore the correlation of immunosuppressive and/or immune-stimulating immune marker profiles at baseline to disease response to therapy (response assessed by RECIST 1.1 and irRECIST criteria) using odds ratios and 95% confidence intervals.
- We will summarize serial changes in immune marker profile in peripheral blood mononuclear cells (PBMCs) from baseline (pre-trial therapy) using mean, standard deviation, median, and inter-quartile range.
- We will plot serial changes in the immunosuppressive and/or immune-stimulating immune marker profile in PBMCs by disease response to therapy (response assessed by RECIST 1.1 and irRECIST criteria)
- We will explore an immune marker or set of markers in circulating PBMCs that corresponds to tumor infiltrating lymphocyte (TIL) percentage in baseline tumor
- In the cohort of patients who have re-biopsy at progressive disease (PD): We will summarize changes in a broad array of immune markers from baseline to time of progressive disease on trial therapy using mean, standard deviation, median, and inter-quartile range.

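### Serial PBMC change is summarised by simple means while on-treatment sampling stops with treatment, so the mean change can rise over cycles by selection alone

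*Combined protocol and SAP*

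**What the plan says.** Objective 1.4.3 is "To characterize serial changes in immune marker profile in peripheral blood mononuclear cells (PBMCs) over the course of the trial treatment". Section 9.6.1 states the matching hypothesis: "We hypothesize that the immune marker profile in the peripheral blood will change over the course of eribulin mesylate +/- pembrolizumab therapy". It adds that a larger rise in blood immune activity should go with better radiographic response.

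For the analysis, Section 13.6.1 says "We will summarize serial changes in immune marker profile in peripheral blood mononuclear cells (PBMCs) from baseline", by mean, SD, median and IQR. A companion item reads "We will plot serial changes in the immunosuppressive and/or immune-stimulating immune marker profile in PBMCs by disease response to therapy". The section lists no visits to be summarised, no longitudinal model, and no rule for patients who leave treatment.

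On collection, Section 9 says "blood draws will be obtained every 3 weeks on treatment days prior to the infusion of study drugs", with a further sample "at the end-of-treatment visit in patients who go off study for progressive disease". For patients who stop for another reason, a sample at later progression is sought but optional (Section 9.1; Section 10, notes n and o). Section 5.7 makes treatment length depend on response, progression and tolerance. Section 13.6 labels all correlative analyses exploratory.

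**The concern.** Who supplies blood at a given cycle depends on outcome, and the plan's own hypothesis links outcome to the marker. If patients with small changes progress sooner, they leave the series first. A simple mean of the remaining patients' changes then climbs with cycle even when each patient's change has been constant since Cycle 2.

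The planned summary cannot separate continuing change within patients from a change in who is still sampled, yet Objective 1.4.3 asks about the former. Nothing in the primary analysis is touched. What is at stake is an apparent immune rise on therapy being carried into later studies, where Section 13.6 intends promising findings to be tested.

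**Working it through.** **Inputs from the documents.** Median PFS 7.1 months (Arm A) and 4.1 months (Arm B), constant hazard, 44 patients per arm (Section 13.2); 21-day cycles (Section 5.1).

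**Assumed.** Progression is a proxy for leaving treatment. The strength of the marker-PFS link appears nowhere in the documents, so a range is used.

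**Reproducing the plan's figure.** Section 13.6.1 gives no number. The medians come from the power statement in Section 13.2 (83%, 70 events, HR 0.58, one-sided alpha 0.1), so that was checked first. Power = Φ(|ln 0.58| × √70 / 2 − 1.2816) = Φ(2.279 − 1.282) = Φ(0.997) = 0.841. With the futility look at 35 events (stop if Z < 0) treated as binding, it is 0.826. Both agree with 83% to within about one point.

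**Step 1: who is still there.** At Day 1 of cycle c, t = (c − 1) × 21 / 30.4375 months and S(t) = 0.5^(t/median). For Arm A at C7, t = 4.14 and 0.5^(4.14/7.1) = 0.668, which is 29 of 44.

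| Visit | t (months) | Arm A | Arm B |
|---|---|---|---|
| C2D1 | 0.69 | 93% (41) | 89% (39) |
| C4D1 | 2.07 | 82% (36) | 70% (31) |
| C7D1 | 4.14 | 67% (29) | 50% (22) |
| C10D1 | 6.21 | 55% (24) | 35% (15) |
| C13D1 | 8.28 | 45% (20) | 25% (11) |

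**Step 2: drift by selection.** Each of 400,000 simulated patients has a fixed change from baseline d, with mean 0 and SD 1, constant from C2 onward. Time to progression is exponential with median 7.1 × exp(βd) or 4.1 × exp(βd), with β from 0.3 to 0.7 (assumed). The true mean change is zero at every visit. Mean d among those still progression-free:

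| Visit | Arm A (β 0.3 to 0.7) | Arm B (β 0.3 to 0.7) |
|---|---|---|
| C4 | 0.06-0.16 SD | 0.11-0.25 SD |
| C7 | 0.12-0.29 SD | 0.21-0.44 SD |
| C13 | 0.23-0.48 SD | 0.39-0.71 SD |

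A different dependence model (Gaussian copula, assumed correlation 0.3 to 0.5 between change and PFS time) gives similar results at C13: 0.26-0.44 SD in Arm A and 0.38-0.64 SD in Arm B.

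**Step 3: size against noise.** With an SD of change of 1, the standard error of an arm mean at C13 is 1/√20 = 0.22 in Arm A and 1/√11 = 0.30 in Arm B. The drift is about one to two standard errors.

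**Step 4: does the alternative help?** At C2 the bias is at most 0.10 SD. With visit noise of SD 0.5 added, visit means from a random-intercept model in Arm B at C13 fall from about 0.39 to 0.06 SD (β 0.3) and from about 0.70 to 0.14 SD (β 0.7). The model improves matters because patients who leave after C2 have already shown their change. It cannot recover those lost before C2. Constant change per patient is also the structure this model fits best.

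**The case against.** The strongest reply is that the plan summarises change from baseline. If no patient changes, paired change averages zero whoever remains; a separate simulation of that case gave at most 0.003 SD in absolute value at any cycle. A reader might infer that a trend would appear with no change within patients at all. That would need raw visit means set against an all-patient baseline, and 13.6.1 does not say this will be done. The drift shown here needs patients to differ in change and that difference to be related to PFS.

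A reader might also infer that blood is taken only during treatment. It is not: the off-treatment draw at progression, and the optional later one, give some early progressors a final paired sample. But each is one sample timed by an event, and 13.6.1 does not say how it enters the serial summary.

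A third tempting reading is that curves compared by arm would mislead. Section 13.6.1 plans no such curves; its only plot is by response. The between-arm gap in drift at C13, about 0.2 SD, is also below the standard error of an arm difference, √(1/20 + 1/11) = 0.38 SD.

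The response plot helps in part, though attrition continues within each response group. Finally, the size rests on an assumed link: Section 9.6.1 hypothesises a correlation with radiographic response, not an effect on time to progression. All of this limits the point; none of it removes the selection.

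**Conclusion.** The point holds in a limited form. A simple mean of change from baseline, taken over whoever is still sampled, mixes continuing change with selection. Under the stated range the selection part is modest at C4 and noticeable by C13, where only about 20 and 11 patients per arm remain progression-free.

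This rests on three assumptions: the exp(0.3) to exp(0.7) effect per SD, change that is constant after C2, and progression as a proxy for leaving treatment. The proxy ignores stopping for toxicity, treatment continued past first progression, and draws during crossover. Section 13.6.1 lists no visits, so using each cycle's Day 1 follows the collection schedule, not a stated analysis plan. With no test or decision attached, the point is minor.

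**What to change.** In Section 13.6.1:

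- Make the main summary the within-patient change from C1D1 to one early fixed visit. C2D1 keeps about 93%/89% of patients and has the least selection. C4D1, near the first restaging, allows more exposure but keeps 82%/70% and carries more drift.
- Describe later cycles with a linear mixed model by randomized arm, with random patient effects, using all visits of initial therapy and leaving out crossover draws.
- Show the number sampled at each cycle beside every table and plot.
- Report the off-treatment progression sample separately, as change from baseline to progression.

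The cost is a few lines of SAP text and a standard model; no extra samples or visits are needed. The downside is less emphasis on raw late-cycle means, and the model reduces the selection without fully removing it.

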#### 13.6.2 *Stool and microbiome correlative science endpoints:*

Overall, we plan to describe the landscape of gut microbiota in patients with BC who will receive pembrolizumab, and the changes in their gut microbiota after two cycles of pembrolizumab. Statistical analyses of intestinal microbiota samples will be performed using R Statistical Language (v3.1.1) and GraphPad Prism (version 6.0e) software packages. Unpaired Mann-Whitney rank sum test (two-tailed) will be used for comparisons of continuous variables between two groups. Bar plots will be used to represent the data's mean at the center values, with error bars to indicate standard deviation. In order to explore the association of response (objective response according RECIST 1.1 and progression-free survival) to baseline microbiota diversity, and changes from baseline in microbiota, inference will be based on Wilcoxon rank sum tests and estimates of predictive value along the continuous scales will be visualized using receiver operating characteristic (ROC) curves and reported with c-index and confidence intervals derived from variance estimates of Somers rank correlation. Unadjusted P-values will be considered significant for the Mann-Whitney rank sum test.

We will quantify microbiome features from amplicon, metagenome, metatranscriptome using established pipelines to identify strain-level taxonomic, functional gene, transcriptional, and microbially-mediated metabolite profiles associated with BC patients with and without immunotherapy. We will use modified multivariate linear modeling to identify statistically significant features associated with outcomes. Statistical tests for association with these outcomes and covariates will be performed using the sparse generalized linear model MaAsLin, which provides random effects models for both log-Gaussian and zero-inflated negative binomial link functions. Computational workflows for these steps are implemented as AnADAMA2 (<http://huttenhower.sph.harvard.edu/anadama>) workflows, a reproducible data handling environment that captures all provenance during the analysis process.

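### Section 13.6.2 specifies no between-arm analysis for microbiome objectives 1.4.9 and 1.4.11, and names a rank-sum test as the inference for censored PFS

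*Combined protocol and SAP*

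**What the plan says.** **Objectives.** In Section 1.4, objectives 1.4.9 (baseline microbiome) and 1.4.11 (change in Shannon index after two cycles) each ask whether the marker "is associated with efficacy of pembrolizumab plus eribulin versus eribulin alone". Objectives 1.4.12 and 1.4.13 ask a different question, about response to the combination itself.

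**Samples.** Section 9 states: "All patients will additionally be asked to provide a stool sample at three separate timepoints". Footnote q of the Section 10 calendar puts these at baseline, around C3D1 and at progression. It takes none during Arm B crossover and does not count a missing sample as a violation.

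**Analysis.** Section 13.6.2 begins: "we plan to describe the landscape of gut microbiota in patients with BC who will receive pembrolizumab, and the changes in their gut microbiota", the changes being those after two cycles of pembrolizumab. It then sets out to "explore the association of response (objective response according RECIST 1.1 and progression-free survival) to baseline microbiota diversity, and changes from baseline in microbiota", and says that "inference will be based on Wilcoxon rank sum tests and estimates of predictive value along the continuous scales" will be shown by ROC curves and a c-index with Somers-type intervals. Its second paragraph turns to microbial features and to "metabolite profiles associated with BC patients with and without immunotherapy", using MaAsLin models with outcomes and covariates. No sentence names a treatment-arm term, a comparison of associations between arms, or an interaction.

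**Status.** Section 13.6 declares all correlative analyses exploratory and hypothesis-generating.

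**The concern.** Whether a marker relates to efficacy of one regimen versus another is a marker-by-treatment question. It is answered by comparing the marker–outcome association between the randomized arms. A test of diversity between responders and non-responders, in Arm A or in the pooled trial, answers a different question: whether diversity goes with good outcome.

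That gap matters for the stated purpose. Section 2.6.2 wants biomarkers that would spare resistant patients the risk of immune-related toxicity, and Section 9.6.1 hypothesizes that "structure and function of gut microbiome changes in response pembrolizumab-based therapy and can predict the likelihood of response to pembrolizumab". Both need a marker of what pembrolizumab adds. Eribulin is given in both arms, so a diversity shift at C3D1 in Arm A may be eribulin's doing. Only Arm B can show that.

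The same sentence lists PFS among the outcomes and then says "inference will be based on Wilcoxon rank sum tests". A rank-sum test compares two groups of fully observed values. PFS is censored, and no rule is given for splitting patients into PFS groups.

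**Working it through.** **1. Objectives against analysis.**

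| Objective | Question | Analysis in 13.6.2 that answers it |
|---|---|---|
| 1.4.9 | Baseline microbiome and efficacy, A versus B | None stated |
| 1.4.11 | Change in Shannon index and efficacy, A versus B | None stated |
| 1.4.12, 1.4.13 | Features or pathways and response to the combination | Within-combination association; MaAsLin |

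The population also differs within the section. Change after two cycles of pembrolizumab can be measured only in Arm A, because no stool is taken on crossover. The second paragraph, however, includes patients without immunotherapy.

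**2. The trial's own figure, as background.** Section 13.6.2 gives no number. The 70 events used in step 4 come from Section 13.2, which states 83% power at HR 0.58 and one-sided alpha 0.1. Check: √70/2 × |ln 0.58| − 1.282 = 4.183 × 0.545 − 1.282 = 0.997, which gives 84.1%. Simulating the futility look at 35 events (stop if Z < 0) gives 82.6%. The stated figure reproduces.

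**3. What the stated test can distinguish.** Illustration with 44 patients per arm, complete stool, a standard-normal marker, log-odds of response 1 per SD, two-sided 0.05 and 1,000 trials per setting. Response rates are those at the mean marker value. The 11% is the eribulin figure quoted in Section 2.4. The other rates and the marker effect are assumptions.

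| Response A / B | True marker effect | Rank-sum, Arm A | Rank-sum, pooled | Interaction (logistic) |
|---|---|---|---|---|
| 11% / 11% | same in both arms | 52% | 83% | 3% |
| 25% / 11% | same in both arms | 74% | 90% | 3% |
| 30% / 30% | same in both arms | 76% | 98% | 4% |
| 11% / 11% | Arm A only | 50% | 30% | 25% |
| 25% / 11% | Arm A only | 73% | 52% | 36% |
| 30% / 30% | Arm A only | 74% | 47% | 45% |

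The Arm A column is the same in both halves apart from simulation error, and must be: Arm A data alone carry no information on what the marker does under eribulin alone. Pooling makes things worse, since it rejects more often for the prognostic marker than for the one that matters only in Arm A.

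The absolute rates depend heavily on the inputs. With odds ratios of 2.0, 2.5 and 3.0 per SD, the Arm A rank-sum rate for a prognostic marker is 44%, 61% and 77% at about 25–28% overall response. At 11% overall response it is 25%, 38% and 47%, and with only 30 stool samples (assumed) 16%, 24% and 31%.

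**4. Precision of an interaction estimate for PFS.** Split the marker at its median and assume equal events in the four arm-by-marker cells. Then SE of the log ratio of hazard ratios = √(4 ÷ (events/4)) = √(16/events).

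- 70 events: SE = √(16/70) = 0.478. Detectable ratio with 80% power: exp((1.960 + 0.842) × 0.478) = 3.8 at two-sided 0.05, and exp((1.282 + 0.842) × 0.478) = 2.8 at one-sided 0.10.
- 35 events (assuming half have usable stool): SE = 0.676, with ratios of 6.6 and 4.2.

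**5. Censoring.** At 70 events in 88 patients, 88 − 70 = 18 patients (20%) have no PFS event. This is not an upper bound on the number censored: Section 13.4 also lets the final analysis be triggered by 12 months of follow-up after the last enrolment, if that comes first. The number with stool is unknown.

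**The case against.** Several counter-arguments have weight.

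- **Arm B is not ignored.** A reader of the opening sentence might infer that only pembrolizumab recipients are studied and that Arm B stool goes unused. The second paragraph contradicts this, and the two groups for the Mann-Whitney test are not named, so an arm comparison is not excluded. MaAsLin could carry an arm term. What stands is that no between-arm contrast of the association with efficacy is specified.
- **PFS has a second measure.** A reader might infer that PFS cannot be analysed properly at all under this plan. That is too strong: the c-index with Somers-type intervals has a censored-data form. But the section does not say that this form will be used, and it assigns inference to the rank-sum test.
- **Some hypotheses are within-combination.** Section 9.6.1 says that baseline diversity predicts efficacy of pembrolizumab and eribulin together. An association within Arm A supports that as written, and it also serves 1.4.12 and 1.4.13. The gap is confined to 1.4.9, 1.4.11 and any reading of the C3D1 change as an effect of pembrolizumab.
- **The work is exploratory and small.** True, and an interaction test would find an Arm-A-only marker in just 25–45% of the simulated trials. That argues for reporting an estimate with its interval, and against expecting a firm answer. It does not make the rank-sum test answer the comparative question. Section 13.6 sends promising findings to future studies, so candidates should be labelled correctly.

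**Conclusion.** The point holds in limited form. Section 13.6.2 specifies no analysis that answers objectives 1.4.9 and 1.4.11, its stated population is inconsistent within the section and with those objectives, and the rank-sum test is not a valid inference for censored PFS without a stated grouping rule. The documents do not support saying that the data cannot answer the objectives: stool is requested in both arms, and Arm B's C3D1 sample is taken before any crossover pembrolizumab.

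Severity is low to moderate. The primary and secondary analyses are untouched, and the correlative work is declared exploratory. The simulated percentages illustrate the difference between prognostic and predictive under assumed response rates, marker effects and complete stool; they do not measure an error in any figure of this trial. The precision figures rest on a median split and equal events per cell.

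**What to change.** 1. State one population in Section 13.6.2, consistent with 1.4.9 and 1.4.11, and say which analyses use Arm A only (1.4.12, 1.4.13 and the baseline-diversity hypothesis).
2. For 1.4.9 and 1.4.11, fit in both randomized arms a logistic model for objective response and a Cox model for PFS, each with arm, Shannon index and arm × Shannon index. Report the interaction with its confidence interval and the within-arm estimates, labelled exploratory.
3. For the C3D1 change, start PFS at a C3D1 landmark and compare the change itself between arms. C3D1 falls at about 6 weeks (two 21-day cycles) and the first scheduled scan at 9 weeks, so few events should be lost. Because the change is affected by treatment, its interaction is descriptive even in a randomized trial.
4. For PFS, replace the rank-sum test with the Cox model or a c-index in its censored-data form. Keep rank-sum tests for binary response as description.

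The cost is SAP wording and a few model runs on samples already requested, with no added visits or patients. The downside is imprecision. With 70 events, the 95% interval for the ratio of hazard ratios spans a factor of exp(1.96 × 0.478) ≈ 2.6 either side of the estimate, and more if voluntary stool is incomplete. The text should say that this is an estimate and not a powered test.
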